13.5.3. Efficacy

Efficacy
Snapshot

 The Snapshot algorithm is intended to be primarily a virologic assessment of the endpoint, and as such follows a “virology first” hierarchy. ‘HIV-1 RNA < 50 c/mL’ or ‘HIV-1 RNA ≥ 50 c/mL’ within an analysis window (see Table 2 and Table 3) is typically determined by the last available HIV-1 RNA measurement in that window while the participant is On-treatment in the Intervention Phase (as assigned based on Section 13.3). When no HIV-1 RNA data is available within a window, a participant cannot be assigned to the category of ‘HIV-1 RNA < 50 c/mL’. Depending on the reason for lack of data, the participant will be classified as ‘HIV-1 RNA ≥ 50 c/mL’ or reported as ‘No Virologic Data at Week X’; in the latter case, the algorithm further classifies the nature of the missing data. Typically, a participant withdrawn (i) due to AE or, (ii) for another reason yet was suppressed at the time, will be counted as ‘No Virologic Data at Week X’. Should a participant withdraw for reasons other than AE and was not suppressed at the time, they will be categorized as ‘HIV-1 RNA ≥ 50 c/mL’. Full details of the algorithm, including the handling of special cases, are included in Appendix 8: Snapshot Algorithm Details.
Plasma HIV-1 RNA

 HIV-1 RNA results may be provided as censored values, such as <40 or >9,999,999 c/mL. For the purposes of summary statistics, such values will be replaced by the next value beyond the limit of detection, e.g., 39 or 10,000,000 c/mL, respectively, for the given examples. Data listings will show the censored values as provided.
Confirmed Virologic Failure (CVF)

 For the purposes of clinical management in this study, CVF is defined as: 
 Rebound as indicated by two consecutive plasma HIV-1 RNA levels ≥ 200 c/mL. The CVF definition is provided in the protocol Section 7.1.7 Only plasma HIV-1 RNA values determined by the central laboratory will be used to assess virologic failure.
CDC Classification for HIV-1 Infection (2014)

 CDC HIV-1 Classification at Baseline is collected in eCRF and no derivation will be performed programmatically for analysis purposes. Please refer to study protocol for detail description of CDC HIV-1 Classification.

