7.1.6. Virologic Failure

Only plasma HIV-1 RNA values determined by the central laboratory will be used to assess virologic failure. The use of local laboratory services to assess virologic failure is only allowed with prior approval (before to initiating the study) obtained by the study team with agreed guidance.

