7.1.7. Definition of Protocol-Defined Confirmed Virologic Failure

For the purposes of clinical management in this study, CVF is defined as:

Rebound as indicated by two consecutive plasma HIV-1 RNA levels ≥200 c/mL.

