7.1.8. Managing Virologic Failure

Following study entry, no changes, or intensification of ART will be permitted prior to protocol-defined virologic failure, outside of the planned protocol regimens. Only plasma HIV-1 RNA values determined by the central laboratory will be used to assess virologic failure (except where the use of a local laboratory for study-specific assessments has been reviewed and approved by the sponsor prior to study start). Baseline plasma HIV-1 RNA is the assessment completed on study Day 1. The definition of confirmed virologic failure does not apply to participants in the LTFU Phase. These participants will be followed for the emergence of viral resistance.

Inadequate adherence or maladministration may be a cause for virologic failure and should be explored as a first step in the management of study participants (e.g., at the first indication of inadequate virologic response or rebound). Upon notification that a participant's HIV-1 RNA plasma level qualifies him/her as a suspected virologic failure (SVF), the Investigator should query the participant regarding intercurrent illness, recent immunization, or interruption of oral therapy.

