Where lab samples are missed in error, including not analysed by the central lab, see the Study Reference Manual (SRM) for guidance on which samples should have subjects brought back in for a central lab retest (local lab only sites require a local retest only).

Should a patient be required to return to site provide a re-test lab sample the lab date should entered in the eCRF under an unscheduled visit, if the re-test is conducted on a day that is different to the scheduled visit.

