4. ANALYSIS POPULATIONS

This RAP defines patient study participants in detail. Analysis populations that pertain to implementation science deliverables are documented in the Evidera SAP.

Population	Definition / Criteria	Analyses Evaluated
All Subjects Screened Population	
 All participants who were screened for eligibility and inclusion in the study 	
 Patient Study Population
Enrolled Population	
 All patient study participants who passed screening and entered the study. 	
 Patient Study Population
Safety	
 All enrolled participants who received at least one dose of CAB + RPV Oral or CAB LA + RPV LA. 	
 Patient Study Population, Safety, Efficacy, Virology, Other Assessments
Long Term Follow-up Population	
 All subjects receiving at least one dose of CAB LA and/or RPV LA who have discontinued CAB LA +RPV LA regimen and have at least one Long Term Follow-up phase clinic visit 	
 Efficacy, Safety

Refer to [Appendix 12](#): List of Data Displays which details the population used for each display.

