7.1.4.1. Statistical Methodology Specification

Endpoint / Variables

 • Proportion of participants with plasma HIV-1 RNA < 50 c/mL at Month 12 using the FDA Snapshot algorithm (Safety population) • Proportion of participants with plasma HIV-1 RNA ≥ 50 c/mL at Month 12 using the FDA Snapshot algorithm (Safety population) • Proportion of participants with protocol-defined confirmed virologic failure (CVF) over time (Safety population) • Incidence of treatment-emergent genotypic and phenotypic resistance to CAB and RPV in patient study participants with CVF (Safety population)
Results Presentation

 • The proportion of participants with HIV-1 RNA < 50 c/mL, HIV-1 RNA ≥ 50 c/mL, and with recorded CVF at each planned visit with corresponding 95% confidence intervals calculated using the Clopper-Pearson exact method. • Proportion of subjects with incidence of treatment-emergent genotypic and phenotypic resistance to CAB and RPV in patient study participants with CVF at each visit with corresponding 95% confidence intervals calculated using the Clopper-Pearson exact method. • Descriptive statistics for the nominal values and change from baseline values in CD4+ cell counts and the CD4/CD8 ratio.
Subgroup Analyses

 • Summary of study outcomes will be repeated for subgroups of interest as specified in Section 5.4.2: Implementation strategy, Participant sex, age group (<50 vs ≥50), race (White, African Heritage, Asian, Other), and CD4 count (<350, ≥350). • The proportion of participants in each Snapshot study outcome category and sub-category will be summarized in which default sub-categories have been expanded to present Covid-19 vs. Non-Covid-19 related impact (as described in Appendix 8).

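### SAP 13.5.3 derives confirmed virologic failure from central-laboratory HIV-1 RNA only, and drops, undeclared, the protocol's exception for approved local laboratories

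*SAP*

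**What the plan says.** **SAP.** Section 13.5.3 gives the CVF rule of two consecutive plasma HIV-1 RNA values of at least 200 c/mL, cites protocol 7.1.7 for the definition, and adds: "Only plasma HIV-1 RNA values determined by the central laboratory will be used to assess virologic failure". No exception follows. Section 7.1.4.1 lists the endpoint as "Proportion of participants with protocol-defined confirmed virologic failure (CVF) over time (Safety population", and section 4 defines that population as "All enrolled participants who received at least one dose of CAB + RPV Oral or CAB LA + RPV LA". The declared departures from the protocol (sections 2.1 and 2.1.1) concern only the analysis populations.

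**Protocol.** Section 7.1.7 defines CVF as "Rebound as indicated by two consecutive plasma HIV-1 RNA levels ≥200 c/mL" and says nothing about the laboratory. The sections on either side do:

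- 7.1.6 has the central-laboratory rule, followed by "The use of local laboratory services to assess virologic failure is only allowed with prior approval".
- 7.1.8 repeats the rule with a parenthesis: "except where the use of a local laboratory for study-specific assessments has been reviewed and approved by the sponsor prior to study start".
- 8.4.4, on samples missed in error, says "local lab only sites require a local retest only". Plasma HIV-1 RNA is among the tests listed in that section.

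**The concern.** The SAP calls its endpoint protocol-defined, but its data-source rule is narrower than the protocol's. At a site that tests only locally there are no central values, so two consecutive central values at or above 200 c/mL cannot exist. Under protocol 7.1.8.3 the same participant can be declared a CVF and discontinued from study treatment. In the analysis that participant counts as a non-failure.

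At stake are the CVF proportions over time (Tables 2.7 and 2.8, the first also a headline output) and the displays conditioned on CVF: Tables 2.9 and 2.10, Figure 2.4 and Listing 12. Table 2.11 summarises genotype and phenotype for participants who did not meet CVF, so a clinically declared local-laboratory CVF with resistance data would appear there. Reported CVF counts could also disagree with the recorded reasons for discontinuation.

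**Working it through.** No figure in the plan is in dispute, so there is none to reproduce. The check is a comparison of text, followed by an illustration of size.

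**Step 1: the rules side by side.**

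| Source | Values used for virologic failure | Approved local laboratory accepted? |
|---|---|---|
| Protocol 7.1.6 | Central | Yes, with prior approval |
| Protocol 7.1.8 | Central | Yes, if approved by the sponsor before study start |
| Protocol 7.1.7 | Not restricted | Silent |
| SAP 13.5.3 | Central | No exception given |

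The SAP's cross-reference goes to 7.1.7, the one section of the three without the exception, so following it does not restore the exception.

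**Step 2: effect on a participant with local values only.** The SAP rule leaves no usable HIV-1 RNA, so the numerator contribution is always 0. The Safety population has no exclusion for laboratory source, so the denominator contribution is 1.

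**Step 3: reach of the rule.** The central-only sentence concerns virologic failure. The Snapshot outcome, also in 13.5.3, "is typically determined by the last available HIV-1 RNA measurement in that window while the participant is On-treatment in the Intervention Phase", and the steps in SAP Appendix 8 contain no laboratory restriction. A local value of 50 c/mL or more can therefore still place the participant in the category of HIV-1 RNA at or above 50 c/mL.

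**Step 4: size.** Inputs from SAP 2.4.1: 18 sites and 450 evaluable patients. Assumptions: equal site sizes, equal CVF risk across sites, and k sites with local HIV-1 RNA only. The documents give neither k nor an expected CVF rate.

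- Patients per site: 450/18 = 25.
- Share of the denominator per local-only site: 25/450 = 1/18 = 5.6%.
- Expected reported proportion = true proportion × (18 − k)/18.

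| k | Factor | Assumed true 1% | Assumed true 2% |
|---|---|---|---|
| 0 | 18/18 | 1.00% | 2.00% |
| 1 | 17/18 | 0.94% | 1.89% |
| 3 | 15/18 | 0.83% | 1.67% |
| 6 | 12/18 | 0.67% | 1.33% |
| 9 | 9/18 | 0.50% | 1.00% |

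In events, a true 1% means 450 × 0.01 = 4.5 expected CVFs. One local-only site removes 25 × 0.01 = 0.25 of them, and three remove 0.75.

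**Step 5: the resistance summary.** Resistance is reported among participants with CVF. A CVF that is not recognised leaves both the numerator (if resistance emerged) and the denominator. The count with resistance can fall, but the proportion can move either way.

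**The case against.** The best defence has four parts.

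1. **No exposed group is shown.** Local testing needs approval, the documents name no approved site, and 8.4.4 mentions local-only sites only in a retest rule that defers to the Study Reference Manual. This stands as a limit on size: if k = 0, nothing changes numerically. It does not reconcile the two texts.
2. **The endpoint is labelled protocol-defined**, so a programmer might apply the protocol's exception anyway. That is possible, but the explicit sentence in 13.5.3 says otherwise and the section it cites does not contain the exception.
3. **Central-only can be a legitimate choice** for consistency of assay. It can, but it would then be a departure to declare, with a stated rule for participants who have no central values.
4. **The consequence is modest.** CVF is a secondary endpoint, summarised descriptively with exact intervals. Withdrawals for lack of efficacy or protocol-defined stopping criteria are tabulated separately, so a mismatch could be noticed. This is fair and bears on priority.

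A reader might also infer more than the documents support:

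- *That these participants escape every failure outcome.* Snapshot carries no such restriction.
- *That everyone at an approved site is affected.* A participant who also has two consecutive qualifying central values can still be counted.
- *That the resistance proportion is biased downwards.* Its direction is undetermined, and the resistance data are not lost, because non-CVF data are displayed too.
- *That 5.6% is the size of the error.* It is one site's share of the denominator under equal site sizes. On the endpoint scale, one such site moves an assumed 1% by 0.06 percentage points.

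**Conclusion.** The inconsistency is real and confined to CVF and the displays conditioned on it. As written, SAP 13.5.3 makes protocol-defined CVF underivable for participants with only local HIV-1 RNA while keeping them in the denominator. It is a wrong rule rather than a missing detail, and it is not declared.

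Any error in the CVF proportion is an understatement, by a relative k/18 under equal site sizes and equal risk. It is zero if no site tests only locally and small in percentage points if few do. With only about 4.5 events expected at an assumed 1%, however, a single missed case would be visible in the result. Whether such sites exist, and how many, has to come from the sponsor. The plan should be corrected, but the documents do not establish that any reported number will be wrong.

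**What to change.** In SAP 13.5.3, state that CVF is derived from central-laboratory HIV-1 RNA and, for sites approved under protocol 7.1.6 and 7.1.8, from local-laboratory HIV-1 RNA. Add a flag to the CVF listing (Listing 12) for CVFs that rest on a local value.

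If a central-only analysis is intended, declare it in SAP 2.1.1 as a change from the protocol, remove participants without central values from the CVF denominator, and report how many were removed.

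The first option costs one sentence and a data-source flag. The second costs one table row and a denominator rule. Neither needs new data collection at sites whose local results are already in the study database. Whether they are is not stated and should be confirmed.

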13.5.4. Safety

Adverse Events
DAIDS Grading

 Clinical adverse events will be graded based on the Division of AIDS Table for Grading the Severity of Adult and Pediatric Adverse Events Version 2.1, March 2017, as specified in the protocol Appendix 10.2. If a grade value is expected per DAIDS but is missing in the eCRF, then the missing grade will be given an ordinal grade value of -1 for determining the maximum grade within and across preferred terms. For example:

Adverse Events

 • if a participant has two separate instances of the same preferred term, one with grade 2 and one with missing grade, then the maximum grade for the preferred term will be set to grade 2. • if a participant reports two different AE preferred terms overall, one with grade 1 and one with missing grade (where a DAIDS grade is expected), then the maximum grade across preferred terms (i.e. in the ANY EVENT row) will be set to grade 1. • If a participant reports only one AE overall and this has a missing grade (where a DAIDS grade is expected), then this will be presented under a grade = missing category
Days since First Dose (Days)

 • AE Start Date – Intervention Phase Treatment Start Date + 1
Days since Last Dose (Days)

 • AE Start Date – Date of Last Dose of Study Treatment (Oral CAB+RPV, SOC bridging, CAB/RPV IM Injection) prior to/on the Start Date of AE + 1
Days since Phase Start

 • For AEs in Intervention/Extension Phase: 
 ○ AE Start Date - Intervention Treatment Start Date + 1 • For AEs in Long-term Follow-up Phase: 
 ○ AE Start Date – LTFU ART Start Date
Duration (Days)

 • AE Resolution Date – AE Start Date + 1
Drug-related

 • If relationship is marked 'YES' on Inform/eCRF • Injection site reactions will be considered as drug-related if the relationship to study drug value is missing in the eCRF.
Laboratory Parameters

 • If a laboratory value which is expected to have a numeric value for summary purposes, has a non-detectable level reported in the database, where the numeric value is missing, but typically a character value starting with '<x' or '>x' (or indicated as less than x or greater than x in the comment field) is present, the number of significant digits in the observed values will be used to determine how much to add or subtract in order to impute the corresponding numeric value. If a character value starting with "<=x", then the numeric value will be x. 
 ○ Example 1: 2 Significant Digits = '< x' becomes x – 0.01 ○ Example 2: 1 Significant Digit = '> x' or '>=x' becomes x + 0.1 ○ Example 3: 0 Significant Digits = '< x' becomes x – 1
Lab Toxicities – DAIDS Grading

 • Toxicities will be based on the Division of AIDS (DAIDS) grading system, Version 2.1, March 2017, as specified in the protocol of Appendix 10.2 • Toxicity grades provided by the central laboratory do not distinguish between abnormally high or low criteria, when both are relevant for a particular parameter.

Other Safety Endpoints
Extent of Exposure

 • Exposure to CAB+RPV (oral lead-in or oral bridging) and CAB LA+RPV LA will be calculated from the IP eCRF pages. 
For Intervention Phase:
 
 • Exposure to CAB+RPV Oral Lead-in = IP (oral lead-in) stop date - IP (oral lead-in) start date + 1 • Exposure to CAB LA + RPV LA = Number of IP injection visits received during the Intervention Phase (up to but not including injections administered at Month 14) • Exposure to SOC oral bridging: Duration of the SOC ART medication taken as oral bridging during the Intervention Phase. If the SOC oral bridging is taken in different periods during the Intervention Phase, the duration will be calculated by the sum of non-overlapped periods. • Exposure to CAB+RPV Oral Bridging (COVID-19 Related): Duration of the CAB+RPV taken as oral bridging for reasons related to COVID-19 during the Intervention Phase. If COVID-19 related CAB+RPV oral bridging is taken in different periods during the Intervention Phase, the duration will be calculated by the sum of the non-overlapped periods. • Exposure to CAB+RPV Oral Bridging (Non COVID-19 Related): Duration of the CAB+RPV taken as oral bridging for reasons not related to COVID-19 during the Intervention Phase. If non COVID-19 related CAB+RPV oral bridging is taken in different periods during the Intervention Phase, the duration will be calculated by the sum of the non-overlapped periods. • Overall Exposure to Study Treatment: min [Date of Latest Intervention Phase Visit up to and including Month 12, max (Date of Last Injection + 63, Date of Last Dose of Oral CAB+RPV, Date of Last Dose of SOC Oral Bridging)] – min (Start Date for Oral lead-in CAB+RPV, Date of First CAB/RPV Injection) + 1 • Overall Exposure to CAB + RPV = Overall Exposure to Study Treatment – Exposure to SOC Oral Bridging 
For Intervention + Extension Phase:
 
 • Exposure to CAB LA + RPV LA = Number of IP injection visits received during Intervention Phase and Extension Phase • Exposure to SOC or CAB+RPV Oral Bridging during the Intervention and Extension Phase will be calculated similarly to that during the Intervention Phase except that the exposure includes both Intervention and Extension Phase. • Overall Exposure to Study Treatment: min [LTFU ART start date, Commercial product Safety Follow-up Visit date, max (Date of Last Injection + 63, Date of Last Dose of Oral CAB+RPV, Date of Last Dose of SOC Oral Bridging)] – min (Start Date for Oral lead-in CAB+RPV, Date of First Study Injection) + 1 • Overall Exposure to IP = Overall Exposure to Study Treatment – Exposure to SOC Oral Bridging • Duration of dosing in participant years will be calculated as the sum of participant duration of dosing in days (across all participants)/365.25

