1. INTRODUCTION

The purpose of this reporting and analysis plan (RAP) is to describe the analyses to be included in the Clinical Study Report for Protocol 213199. This RAP is based on the original protocol (Dated 06-MAY-2020) of study GSK1265744/213199 (GSK Document Number [2019N420690_01](#)) and its protocol amendments 01 (Dated 02-DEC-2020, GSK Document Number [2019N420690_02](#)) and 02 (Dated 24-MAY-2021, GSK Document No. TMF-13794092).

GlaxoSmithKline Document Number	Date	Version
TMF-11899418	12-MAR-2021	Original
TMF-15213711	30 Nov 2022	Amendment No. 1

The reasons for this amendment were to: plan specific outputs related to participant pregnancy in line with protocol amendment 02; add clarity on the Covid PD impact on exposure formula; Adjust on treatment definition to add 63 days post injection instead of 35; Additional categories added to summarize oral exposure to Oral Bridging (Covid and Non-Covid related); if SOC ART started immediately after missed injection, then injection would not be count as missed. Clarity added around entry into LTFU and transition to commercial product. List of displays for EOS updated to account for pregnancy and RAPIDO Data Viewer.
		

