1.1. RAP Amendments

Revision chronology:

RAP Section	Amendment Details
Reporting and Analysis Plan (RAP) CARISEL_213199_Final [12-MAR-2021]	
Reporting and Analysis Plan (RAP) CARISEL_213199_Amendment_1 [30 Nov 2022]	
Inclusion of additional pregnancy based output	
 Protocol amendment 02 allows pregnant participants to continue on study. Listings have been added to address pregnancy specific events.
Data Handling	
 Pregnancy data accommodations have been added. Exposure formulas were adjusted to account for Q8W dosing, protocol deviation impact, transition to commercial product, and various scenarios related to Oral Bridging or missed injections.
Data Displays	
 Display status for EOS was updated to consider use of the RAPIDO Data Viewer. The following displays were added for pregnancy summarization: Listings 49-57

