13.12. Appendix 12: List of Data Displays

All data displays will use the term “subject” rather than “participant” in accordance with CDSIC and GSK Statistical Display Standards.

Where applicable, all summary displays will present data across both the Intervention and Extension phases unless explicitly stated otherwise in the display title.

At EOS, the RAPIDO Data Viewer will be produced to allow for the clinical team to review ADaM data directly related to adverse events, exposure, HIV-1 RNA, and labs. This will take the place of some, previously standard generic listings from these categories. Listings including results of pregnancy details will only be included if a pregnancy occurs.

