13.12.7. Safety Tables

Safety: Tables					
No.	Population	GSK Standard/ Example Shell	Title	Programming Notes	Deliverable
Exposure					
3.1.	Safety	207966/primary_15/T3.1	Summary of Exposure to Study Treatment by Implementation Arm (Intervention Phase)	Includes Oral Bridging	IA2, M12
3.2.	Safety	207966/primary_15/T3.1	Summary of Exposure to Study Treatment by Implementation Arm	Includes Oral Bridging	M12, EOS
3.3.	Safety	SAF T1	Summary of Adherence to CAB LA + RPV LA Dosing Schedule by Visit, Country, and Site (Intervention Phase)	See Section 13.5.2 for Covid Impact Remove Covid-19 impact results from IA1.	IA1, IA2, HL, M12
3.4.	Safety	SAF T2	Summary of Adherence to CAB LA + RPV LA Dosing Schedule by Visit and Subgroup (Intervention Phase)	See Section 13.5.2 for Covid Impact Include all subgroups listed in Section 5.4.2 except for Site & Country	HL, M12
3.5.	Safety	SAF T1	Summary of Adherence to CAB LA + RPV LA Dosing Schedule by Visit, Country, and Site	See Section 13.5.2 for Covid Impact	EOS
3.6.	Safety	SAF T2	Summary of Adherence to CAB LA + RPV LA Dosing Schedule by Visit and Subgroup	See Section 13.5.2 for Covid Impact Include all subgroups listed in Section 5.4.2 except for Site & Country	EOS

CONFIDENTIAL

213199

Safety: Tables					
3.7.	Safety	Study 201584 (primary_02): Table 3.114	Summary of Categorized Needle Length and Gauge for CAB Injection		M12, EOS
3.8.	Safety	Study 201584 (primary_02): Table 3.115	Summary of Categorized Needle Length and Gauge for RPV Injection		M12, EOS
Adverse Events (AEs)					
3.9.	Safety	AE99	Adverse Event Overview by Study Phase and Overall	High level summary to include counts of overall AEs, Serious AEs, AEs leading to withdrawal, related AEs, AEs related to Covid-19, AEs related to Covid-19 leading to withdrawal, fatal AEs Overall breakdown to be condensed to Int + Ext phases.	HL, M12, EOS
3.10.	Safety	AE3	Summary of Adverse Events by Overall Frequency	ICH E3	M12, EOS
3.11.	Safety	AE5B	Summary of Adverse Events by System Organ Class and Maximum Grade	ICH E3	HL, M12, EOS
3.12.	Safety	AE5B	Summary of Adverse Events by System Organ Class and Maximum Grade — Excluding Study Drug Injection Site Reactions		M12, EOS
3.13.	Safety	AE5B	Summary of Adverse Events by System Organ Class and Maximum Grade (Oral Lead-in Period)		M12
3.14.	LTFU	AE5B	Summary of Adverse Events by System Organ Class and Maximum Grade (Long Term Follow-up Period)		M12, EOS

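### The pooled Intervention + Extension exposure formula has no data cut-off or death bound, so at Month 12 nearly every on-schedule ongoing participant is credited with days after the cut

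*SAP*

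**What the plan says.** SAP 13.5.4 (Extent of Exposure) gives two formulas for overall exposure to study treatment.

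- **Intervention Phase only.** The end date is "min [Date of Latest Intervention Phase Visit up to and including Month 12, max (Date of Last Injection + 63" days, last oral CAB+RPV dose, last SOC bridging dose). The first term is an observed visit, so exposure cannot run past it.
- **Intervention + Extension.** The end date is "min [LTFU ART start date, Commercial product Safety Follow-up Visit date, max (Date of Last Injection + 63" days, with the same two oral terms inside the max. The visit term is gone. The only bounds left are the start of LTFU ART and the Safety Follow-up visit held on transition to commercial product.

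The same section then states that "Duration of dosing in participant years will be calculated as the sum of participant duration of dosing in days" across all participants, divided by 365.25.

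In SAP 13.12.7, Tables 3.1 and 3.2 share the title "Summary of Exposure to Study Treatment by Implementation Arm". Table 3.1 adds the Intervention Phase qualifier and is delivered at the second interim and Month 12. Table 3.2 has no qualifier and is delivered at Month 12 and end of study. SAP 13.12 says that "all summary displays will present data across both the Intervention and Extension phases unless explicitly stated otherwise in the display title".

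The 63 days came in with SAP Amendment 1, whose stated reasons include "Adjust on treatment definition to add 63 days post injection instead of 35" (SAP 1) and "Exposure formulas were adjusted to account for Q8W dosing" (SAP 1.1).

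**The concern.** A participant still receiving injections at the Month 12 analysis has not started LTFU ART and has had no commercial-product Safety Follow-up visit. Both outer bounds are missing, so the formula returns last injection + 63 days. That date takes no account of when the data were cut. Nor does the formula contain a date of death or last contact, so someone who dies or is lost soon after an injection, with neither bounding date, is also credited with the full 63 days.

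At stake is a standard safety-report figure: duration on study treatment and total participant-years. As written, the Month 12 version of Table 3.2 would include time that nobody has observed. It would also disagree with Table 3.1 in the same package, and a reader could take the difference for Extension Phase exposure.

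**Working it through.** **1. The 63 days.** The SAP cites Q8W dosing but does not write out the sum. It reproduces as 8 weeks × 7 + a 7-day window = 63; the superseded 35 is 4 × 7 + 7. This derivation is inferred.

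**2. Spacing of injections.** Protocol 4.3.3 and 6.5.3 fix a calendar target date set by the first injection, then dosing every two months from Dose 3 with a ±7-day window. Two-month steps on a fixed date are 59 to 62 days apart.

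**3. On-schedule participant at the cut.** Let d be days since the last injection. On schedule, d never exceeds 62. Days credited beyond the cut = 63 − d, which is at least 63 − 62 = 1 and at most 63 (cut on an injection day).

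**4. Worked participant.** Day 1 is 4 Jan 2021, Dose 1 is 4 Feb 2021, and the Month 12 injection and the data cut are both 4 Jan 2022.
- Intervention formula: 4 Jan 2022 − 4 Jan 2021 + 1 = 366 days.
- Pooled formula: 366 + 63 = 429 days.
- Difference: 63 days, or 63/366 = 17%, with no Extension time in between.

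**5. Average excess.** Assume d is uniform on 0 to 61 days. The mean of 63 − d is 63 − 30.5 = 32.5 days.

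**6. Effect of the dosing window.** If one injection is 7 days early and the next 7 days late, the gap can reach 62 + 14 = 76 days, so some participants will be more than 63 days past their last injection. A simulation gauged how many. It assumed 450 participants all ongoing, uniform enrolment over 3, 6 or 9 months, and a cut 0 or 28 days after the last Month 12 visit.

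| Injections | Share credited beyond the cut |
|---|---|
| On target | 100% |
| Uniform within the window | 96–98% |

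Across all settings the mean excess was about 29 to 41 days.

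**7. Participant-years, as illustration only.** With 400 ongoing, 400 × 32.5 / 365.25 = 35.6 participant-years. The simulation with all 450 ongoing gave about 36 to 51 on a true 503 to 653, or 6–10%. The number ongoing, the enrolment period and the cut date are all assumptions; SAP 3.2 lists the steps before the Month 12 analysis but sets no cut-off date.

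**8. After the fix.** With the cut-off inside the min[], the worked participant has 366 days and the excess beyond the cut is zero by construction.

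**The case against.** **Scope at Month 12.** SAP 8 says Month 12 safety outputs cover the Intervention Phase unless otherwise specified. That leaves the scope less than fully settled. However, the general rule in SAP 13.12, and the pairing of a qualified Table 3.1 with an unqualified Table 3.2 in the same delivery, are such a specification. If Table 3.2 were Intervention only at Month 12, it would duplicate Table 3.1.

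**A bounded figure is already produced.** This is true: Table 3.1 is capped at an observed visit and is delivered at Month 12. It limits the harm but leaves Table 3.2 wrong.

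**The drug has already been given.** A reader might infer that the formula invents exposure. It does not overstate drug administered, and 63 days matches the on-treatment window in SAP 13.3.2. What it overstates is elapsed time on treatment. The pharmacological tail does not explain the rule, since the same formula stops at LTFU ART start or the Safety Follow-up visit, when drug is still present. SAP 13.3.2 also applies its last-injection rule only to participants who permanently discontinued; the exposure formula has no such condition.

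**Adverse event rates.** A reader might infer that event rates are diluted. The documents do not support that: the adverse event displays visible in SAP 13.12.7 are counts and percentages of subjects, or occurrences, with no exposure-adjusted rate.

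**Numbers affected.** Leavers for commercial product are capped by a Safety Follow-up visit about 2 to 4 weeks after the last dose (Protocol 4.5.1.2), and Protocol 4.2.6.4 expects early availability in Germany. The number ongoing could be well below 400. This stands against any headline total, but not against the per-participant error.

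**Timing.** The amendment is dated 30 Nov 2022, and some Month 12 items still use 35 days (the Snapshot steps in SAP 13.8; Figure 2.3). Month 12 may already have been reported under a 35-day rule; the documents do not say. With 35 days and the same uniform assumption, the mean excess would be 35²/(2 × 61) ≈ 10 days. The current SAP still lists Table 3.2 for Month 12.

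**Conclusion.** The derivation is wrong as written, with a limited consequence. Applied at Month 12, it gives nearly every on-schedule ongoing participant exposure beyond the data cut: up to 63 days each, averaging about 32 if the cut falls uniformly within the dosing cycle. The exceptions are participants already capped by one of the two bounding dates, and those more than 63 days past their last injection through late dosing or oral bridging.

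The affected output is Table 3.2 with its participant-years. At end of study only deaths and losses with no LTFU ART start or Safety Follow-up date remain affected. No efficacy result, and no planned adverse event count or percentage, changes. A figure of 6–10% excess exposure should not be presented as a finding about this trial; it holds only under the assumed enrolment, cut date and number ongoing.

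**What to change.** In SAP 13.5.4, change the end date in the Intervention + Extension formula to the minimum of:

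- LTFU ART start date;
- commercial-product Safety Follow-up visit date;
- analysis data cut-off date;
- date of death;
- date of last contact, only for participants lost to follow-up or withdrawn without an LTFU ART start or Safety Follow-up date;
- max(last injection + 63, last oral CAB+RPV dose, last SOC bridging dose).

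The restriction on last contact matters. Applied to everyone, it would make the cut-off redundant and could pull an ongoing participant's exposure back to the last visit. State in SAP 3.2 which date serves as the Month 12 cut-off. Overall exposure to IP and the participant-years follow automatically.

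The cost is up to three extra dates in one derivation, with no change to trial conduct. Stated exposure in Table 3.2 becomes smaller. If Month 12 has already been reported, check which version of the formula was used and footnote or rerun the table.
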